7.5.6 Overall Survival

Overall survival (OS) is defined as the time from randomization (date of complete of Randomization File) until death from any cause (as recorded in Death Report). The

living patients will be censored as the date of last disease assessment (as defined in Section 7.5.1).

The number of patients who died and cause of death will be summarized (**Table 29**) and the Kaplan-Meier curve for the OS in each treatment arm will be displayed (**Figure 5**). The analysis of overall survival will be done using a similar methodology for EPRFS and RFS (**Table 30**).

7.5.7 Rates of Sentinel Node Detection, Parametrial Involvement, Margins Involvement, and Pelvic Nodes Involvement

Rate of sentinel node detection, parametrial involvement, involvement of surgical margins and pelvic node involvement is defined as the proportion of all intention-to-treat patients with respectively metastatic nodes detected in any of the node sites by sentinel or non-sentinel lymph nodes assessment (from Sentinel Lymph Nodes Assessment and Non-Sentinel Lymph Nodes Assessment sections of Surgery Report), tumour present in the parametrium (from Tumor Description section of Surgery Report), resection margins involved (from Tumor Description section of Surgery Report), metastatic nodes detected in node sites of pelvic NOS left and pelvic NOS right by sentinel or non-sentinel lymph nodes assessment (from Sentinel Lymph Nodes Assessment and Non-Sentinel Lymph Nodes Assessment sections of Surgery Report). Two-sided exact confidence intervals will be calculated and a two-sided Fisher's exact test will be used compare these rates between two treatment groups (**Table 31**).

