Mapping of SNs has been recently studied in cervical cancer. Pooled data from 20 studies that include 802 cases show a sensitivity of 93% and a false-negative rate of 6.8% [Levenback 2008]. Hauspy challenged these false negative results and determined that the true false negative rate is closer to 2%. Major causes of false negativity related to inadequate technique including limited or incomplete data on the laterality of the SN detection versus the side of the positive node, unilateral SN detection only and evaluation of only macroscopically involved nodes [Hauspy 2007]. The SN mapping technique has been shown to be more effective when lesions measure < 2 cm and Rob has reported a detection rate of 100% and false negative rate of 0% in patients with lesions measuring < 2cm using a combined technique that incorporates blue dye and technetium⁹⁹ [Rob 2005]. The SN literature also demonstrates that in low-risk patients, the status of the SN is highly correlated with the risk of parametrial invasion [Strnad 2008]; Strnad reported no parametrial invasion in 53 patients with early cervical cancer and negative SN results [Strnad 2008].

A recent publication suggests that SN mapping may be more accurate than standard lymphadenectomy because SNs submitted for pathological evaluation are identified through an ultrastaging procedure [Gortzak-Uzan 2010]. In a subgroup of 36 patients with cervical cancer with bilateral negative SNs, final pathology evaluating ultrastaging-negative nodes did not identify metastasis in those non-sentinel nodes (false positive rate 0) [Popa 2006]. Euscher has reported a 25% increase in the detection of lymph node metastasis in patients with cervical cancer who undergo an ultrastaging procedure [Euscher 2008]. Similarly, Marchiole identified micrometastasis in 5/26 patients (19%) following ultrastaging and serial pathologic sectioning and immunohistochemistry [Marchiole 2005]. The clinical significance of micrometastasis discovered by ultrastaging remains unsettled, but accumulating evidence suggests that micrometastasis may be associated with increases in recurrence rate and inferior disease-free and overall survivals [Marchiole 2005; Horn 2008; Juretzka 2004; Darai 2008; Cibula 2012]. Additional advantages of the SN mapping may be the detection of unusual or aberrant lymphatic drainage to the common iliac or low para-aortic regions, which are areas not routinely sampled with pelvic lymphadenectomy [Rob 2005; Plante 2003; Roy 2011].

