In patients with low-risk disease, SN mapping is an attractive alternative to reduce the morbidity of the complete lymph node dissection. This trial will provide the opportunity to determine the rate of SN detection in patients with lesions < 2cm, the proportion of micrometastasis.

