7.2 Stratification

Subjects will be stratified by:

1. Cooperative Group
2. Intended use of sentinel node mapping (yes vs. no)
3. Stage (IA2 vs. IB1)
4. Histological type (squamous vs. adenocarcinoma/adenosquamous)
5. Grade (1-2, vs. 3 vs. not assessable)

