8.0 TREATMENT PLAN

Although the Canadian Cancer Trials Group acts as the coordinating agency for the trial, the responsibility for treatment of patients rests with the individual investigator. Specific details related to trial conduct by each participating GCIG group are included in the Group-Specific Appendix provided by each Group.

After randomization, protocol-assigned surgery must take place within 8 weeks.

Regardless of when the patient is randomized, protocol surgery must be performed within 20 weeks of the date of the initial pathologic diagnosis (NO EXCEPTIONS). A schema of the treatment plan is shown below.

The decision regarding the use of SN lymph node mapping must be made at the time of randomization.

* Regardless of treatment assignment, surgery will include pelvic lymph node dissection with optional sentinel lymph node (SN) mapping. If SN mapping is to be done, the mode is optional, but the laparoscopic approach is preferred.

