8.2 Lymphadenectomy and Sentinel Node Mapping

Protocol therapy on both treatment arms will include pelvic lymph node dissection. Centres may choose to perform sentinel node mapping for some or all of their CX.5 patients if that is part of their usual practice. For centers not performing sentinel node mapping, a complete pelvic node dissection is considered protocol therapy. All the nodes are submitted for routine pathological analysis as per the Surgery/Pathology Manual. Frozen section analyses of sentinel nodes are not permitted for this trial unless the node is visually suggestive of metastatic spread.

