7.4.6 Sentinel Node Mapping and Lymph Node Dissection

- Success of protocol-defined sentinel node mapping: yes, no, not applicable (**Table 19**)
- Reason for unsuccessful protocol-defined sentinel node mapping: technical reasons, patient refusal, allergy to blue dye, other reason (**Table 19**)
- Technique for sentinel node mapping: laparoscopic, open (**Table 19**)
- Pelvic node dissection done: yes, no (**Table 19**)
- Technique of pelvic node dissection: laparoscopic, open (**Table 19**)
- Para aortic lymph node dissection done: yes, no (**Table 19**)
- Technique of para aortic lymph node dissection: laparoscopic, open (**Table 19**)

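### SAP 7.5.7 defines sentinel node detection as nodal metastasis in all randomized patients, and counts pelvic node involvement only at the two pelvic NOS sites

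*SAP*

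**What the plan says.** SAP 7.5.7 names four rates (sentinel node detection, parametrial involvement, margin involvement, pelvic node involvement) and defines them in that order, linked by *respectively*, as proportions of all intention-to-treat patients. The first numerator is "metastatic nodes detected in any of the node sites by sentinel or non-sentinel lymph nodes assessment". The fourth is "metastatic nodes detected in node sites of pelvic NOS left and pelvic NOS right by sentinel or non-sentinel lymph nodes assessment". Each rate gets an exact confidence interval and a two-sided Fisher test, and Table 31 prints them for the intention-to-treat and per-protocol sets.

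The protocol lists sentinel node detection and pelvic node involvement as separate secondary endpoints (Section 1.2). Its Section 2.3 cites a series with "a detection rate of 100% and false negative rate of 0% in patients with lesions measuring < 2cm" and says the trial will allow determination of "the rate of SN detection in patients with lesions < 2cm, the proportion of micrometastasis". Mapping is optional: "Centres may choose to perform sentinel node mapping for some or all of their CX.5 patients" (Section 8.2). The choice is fixed early: "The decision regarding the use of SN lymph node mapping must be made at the time of randomization" (Section 8.0), and intended mapping is a stratification factor (Section 7.2).

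Elsewhere, SAP 7.4.6 (Table 19) tabulates "Success of protocol-defined sentinel node mapping: yes, no, not applicable" for all treated patients, and SAP 7.4.7 (Table 20) summarises nodes removed and metastatic nodes site by site.

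**The concern.** A detection rate says how often mapping finds a sentinel node. The SAP's numerator says how often cancer is found in a node, whether or not that node is sentinel and whether or not the patient was mapped. Programmed literally, a prespecified secondary endpoint would be reported, with an exact interval and a p-value, as a different quantity under its own name.

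The pelvic row has a separate problem. Restricting it to the NOS (not otherwise specified) codes could leave out metastases recorded at a named pelvic site, so pelvic node involvement could be under-reported. The per-protocol rows add a third: that set removes some of the patients whom the nodal rates are meant to count.

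**Working it through.** The documents give no planned value for these rates, so there is no figure to reproduce. The check compares the definitions and then sizes the effect.

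**1. What the detection row counts.** Matching endpoints to definitions in order leaves only one reading. A mapped patient whose sentinel nodes are found and negative counts as not detected. An unmapped patient with a positive non-sentinel node counts as detected. The pelvic NOS sites are a subset of all node sites, so every patient in the pelvic row is also in the detection row. The two rows are nested metastasis rates and neither measures mapping.

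**2. What the protocol means.** A cited detection rate of 100%, beside a false-negative rate, cannot be a metastasis rate in disease where nodal risk is put below 5% (Protocol 2.1.1). Section 2.3 also names detection and micrometastasis as two quantities.

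**3. Size, detection row as written.** It prints the any-site nodal positivity rate. Inputs: below 5% for low-risk disease (Protocol 2.1.1), and 5/60 = 8.3% in the prospective simple hysterectomy series (Protocol 2.2.3; exact 95% CI 2.8% to 18.4%). With the planned N of 700:
- 0.05 × 700 = 35 patients
- 5/60 × 700 = 58 patients
- 0.023 × 700 = 16 patients, using the 2.3% cited for stage IA2 (Protocol 2.3)

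**4. Correcting only the numerator.** With all randomized patients as denominator, the printed rate is m × d, where m is the share mapped and d the true detection rate among them. The documents give neither for this trial; these values are assumptions.

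| m | d = 0.90 | d = 1.00 |
|---|---|---|
| 0.25 | 22.5% | 25% |
| 0.50 | 45% | 50% |
| 0.75 | 67.5% | 75% |

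The denominator must therefore change as well.

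**5. Pelvic node row.** Results are held by site (SAP 7.4.7). Table 20 shows at least one named site, bifurcation left, and its note treats pelvic NOS left and right as distinct sites. The protocol's dissection covers common, external and internal iliac and obturator nodes (Section 8.2.1), and Section 10.1.1 counts common iliac nodes as pelvic. If a share s of node-positive patients carries a positive NOS code, the row prints (true rate) × s:

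| s | true 5% (35/700) | true 8.3% (58/700) |
|---|---|---|
| 0 | 0% | 0% |
| 0.25 | 1.25% | 2.1% |
| 0.50 | 2.5% | 4.2% |
| 0.75 | 3.75% | 6.25% |
| 1 | 5% | 8.3% |

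At s = 1 there is no error.

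**6. Per-protocol rows.** SAP Section 6 excludes patients found to have more advanced disease on mapping, node dissection or other intraoperative findings. With k node-positive among n patients, removing e node-positive patients gives (k − e)/(n − e), which is below k/n whenever e > 0 and k < n. The set definition therefore lowers the nodal rates.

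**7. Parametrial row (note only).** The simple arm removes no parametria, so its rate is close to zero by design. Taking it as 0/350, Fisher's p is 0.062 for 5/350 against 0/350 and 0.031 for 6/350. The chance of six or more among 350 is 0.3%, 2.0% and 2.5% at the rates cited in Protocol 2.2.2 (0.4%, 0.6%, 0.63%), and 14% only at the 1% upper bound in Protocol 2.1.1. This does not call for changing the test.

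**The case against.** The strongest reply is that mapping performance is reported anyway. Table 19 gives success, technique and reasons for failure by arm, with a not-applicable category that seems to separate unmapped patients, and Table 20 gives sentinel nodes removed per site. This stands to the extent that the information is not lost. It does not repair the endpoint: success is undefined, Table 19 covers only patients who had a hysterectomy (a gap that is probably small), Table 20 is by site and not by patient, and the exact interval and Fisher test are attached to the Table 31 row.

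The protocol also never formally defines detection; its meaning comes from the background section. That is fair, but the 100% figure and the separate listing of endpoints leave no room for a metastasis reading.

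On the pelvic row, the site list is not in the documents, and NOS may be the usual code for routine dissection results. The 0-to-100% sweep shows only that s is unknown. This is correct, so that part is a conditional point to check against the form and not a demonstrated under-count.

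On the per-protocol rows, the exclusion can be read as covering intraoperative findings only. Frozen section of sentinel nodes is restricted (Protocol 8.2), so patients found positive only on final pathology could stay in. The effect may then be modest, but its direction is the same.

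**Conclusion.** The concern holds. The detection definition is wrong as written, and this rests on the text alone. The row would show roughly 5% to 8% if nodal positivity matches the cited low-risk figures, and less if it is nearer the 2.3% cited for stage IA2. The cited 100% comes from one series with a combined tracer and is an upper reference, not an expectation for this trial. Pelvic node involvement may be under-counted by anything from none to all of the cases, depending on how the Surgery Report codes nodes. Per-protocol nodal rates are lowered by the exclusion, by an amount the documents do not allow one to size. The primary non-inferiority analysis does not use these rates. The definitions should be corrected before Table 31 is produced.

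**What to change.** In SAP 7.5.7:

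- **Detection.** Define the rate as patients with at least one sentinel node identified, divided by patients in whom mapping was attempted. Define attempted, because SAP 7.4.6 lists patient refusal and dye allergy as reasons for unsuccessful mapping.
- **Between-arm test.** Use patients with mapping intended at randomization for the Fisher test, and report that rate as a sensitivity figure. Intention is fixed at randomization and is a stratification factor, so the randomized comparison is kept.
- **Any-node metastasis.** If wanted, keep it as a separately labelled rate.
- **Pelvic node involvement.** Count a metastatic node at any pelvic site on the Surgery Report, NOS included, and list the sites following Protocol 10.1.1 (common iliac in, para-aortic out). If the form records every pelvic result under NOS, say so and leave the rule.
- **Table 31.** Footnote the per-protocol rows to say that patients with more advanced disease found on mapping or node dissection are excluded.
- **Wording.** Protocol 1.2 sets out to observe these rates, while Protocol 14.1 and 14.2 and SAP 3.2 compare them; reconcile the two. The parametrial test can stay as it is.

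The cost is one or two sentences, a footnote, a check of the site list and Table 31 programming. Mapping success and nodes by site are already summarised for Tables 19 and 20, and intended mapping is in the randomization file. The only downside is a detection denominator smaller than the intention-to-treat set.

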1.2 Secondary Objectives

- To compare the two treatment arms with respect to:
 - Pelvic relapse-free survival
 - Extra pelvic relapse-free survival
 - Relapse-free survival (any site)
 - Overall survival
 - Treatment-related adverse events
 - Patient Reported Outcomes including global quality of life and measures of sexual health
 - Cost-effectiveness and cost-utility

- To observe rates of the following in this patient population:
 - Sentinel node detection
 - Parametrial involvement
 - Involvement of surgical margins
 - Pelvic node involvement

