8.1 Hysterectomy Procedure

Patients meeting the entry criteria will be randomized prior to surgery to either undergo a radical hysterectomy and bilateral pelvic node dissection or simple hysterectomy and bilateral pelvic node dissection. It is understood that both types of hysterectomy are to be performed by a trained gynecologic oncologist.

All patients entered on this study are expected to undergo their assigned treatment as per the details below. In some cases, obvious evidence of lymph node involvement or extrauterine spread may be detected during surgery. If this occurs, then protocol-mandated surgery may be abandoned (see section 8.2.4 for further details).

All patients should be managed with prophylactic antibiotics and anticoagulants pre and post-operatively as per local institutional standards.

Arm 1 - Radical Hysterectomy (Type 2)

This procedure may be performed abdominally, laparoscopically, robotically or vaginally. The uterus, cervix, medial 1/3 of parametria, 2 cm of the uterosacral ligaments and upper 1-2 cm of the vagina are to be removed *en bloc*. The uterine artery is ligated laterally to the ureters and the ureters are unroofed to the ureterovesical junction.

Arm 2 – Simple Hysterectomy (Extrafascial Hysterectomy)

This procedure may be performed abdominally, laparoscopically, robotically or vaginally. Extradascial hysterectomy involves removal of the uterus with cervix without adjacent parametria. The uterine arteries are transected medial to the ureters at the level of the isthmus and the uterosacral ligaments are transected at the level of the cervix. Surgeons should pay special attention to make sure that the whole cervix is removed. As such, a maximum 0.5 cm of vaginal cuff can be removed to ensure the complete removal of the cervix.

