Other secondary efficacy endpoints include (1) overall survival, defined as time from randomization to the time of death from any cause. Patients who are alive at the time of the final analysis or who have become lost to follow-up will be censored at their last contact date; and (2) extra pelvic relapse-free survival free survival, defined as time from randomization to the time of first documented relapse outside the pelvic field. Patients who had pelvic relapse or died before extra pelvic relapse will be censored at time of pelvic relapse or death. Patients who are alive without any recurrent disease at the time of the final analysis will be censored at their last disease

assessment dates. Analyses for these secondary efficacy endpoints will be done using similar methodology for PRFS. For the rest of the secondary endpoints, the rate of sentinel node detection and rate of parametrial, margins and pelvic nodes involvement, they will be compared between two arms using a Fisher's exact test.

All patients who have received study treatment will be included in the adverse events analysis based on arms they are treated. Adverse events will be graded using the NCI Common Toxicity Criteria Version 4.0. The incidence of adverse events will be summarized by type of adverse event and severity. A Fisher's exact test will be used as needed to compare adverse events between the two arms.

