7.4.5 Results of Tumor Assessment after Hysterectomy

- Cervical cancer detected in hysterectomy specimen: yes, no (**Table 18**)
- Histologic tumour type: squamous, adenocarcinoma, adenosquamous (**Table 18**)
- Histologic grade: 1, 2, 3, not assessable (**Table 18**)
- Depth of stromal invasion: median, min-max (**Table 18**)
- Location of stromal invasion: inner half cervical wall, outer half cervical wall (**Table 18**)
- Horizontal spread/greatest diameter: median, min-max (**Table 18**)
- Lymphovascular invasion: yes, no, undetermined (**Table 18**)
- Resection margins involved: yes, no (**Table 18**)
- Presence of associated intra-epithelial lesion: yes, no (**Table 18**)
- Presence of tumour in the parametrium: yes, no, not applicable (**Table 18**)
- Location of tumour in the parametrium: in continuity with tumour, in lymphovascular space, in parametrial lymph node (**Table 18**)

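### Parametrial involvement is compared between arms over all randomised women, although simple hysterectomy leaves the parametrium in place and so cannot show it

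*SAP*

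**What the plan says.** Protocol 8.1 defines the two operations by, among other things, what happens to the parametrium. In Arm 1 the tissue removed en bloc includes the "medial 1/3 of parametria, 2 cm of the uterosacral ligaments". Arm 2 "involves removal of the uterus with cervix without adjacent parametria".

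In SAP 7.5.7 each pathology rate "is defined as the proportion of all intention-to-treat patients with" the finding in question. For this endpoint the finding is tumour in the parametrium, taken from the Tumor Description section of the Surgery Report. Two-sided exact confidence intervals follow, and then "a two-sided Fisher's exact test will be used compare these rates between two treatment groups". Table 31 sets this out with a simple column, a radical column and a p-value, first for intention-to-treat and then for per-protocol patients. Protocol 14.2 plans the same comparison: "rate of parametrial, margins and pelvic nodes involvement, they will be compared between two arms using a Fisher's exact test".

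Elsewhere the SAP recognises that the item may not be assessable. SAP 7.4.5 lists "Presence of tumour in the parametrium: yes, no, not applicable", although the Table 18 shell prints only No and Yes. Table 14 records whether the hysterectomy was done with or without parametrium.

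The documents disagree about the purpose. Protocol 1.2 places this endpoint under the line "To observe rates of the following in this patient population", apart from the between-arm comparisons. Protocol 14.1 and SAP 3.2 list it among the comparisons, and the background in Protocol 2.2.3 also speaks of comparing it.

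**The concern.** An involvement rate can be compared between arms only if the tissue is examined in both. Here the randomised treatment decides whether it is examined. Section 7.5.7 does not take women without an assessable parametrium out of the denominator, so they enter as non-events. The SAP does not say this in words; it follows from the all-randomised denominator. Women in either arm who had no hysterectomy enter in the same way.

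The simple column of Table 31 would then be close to zero by design, with a tight interval around it. That looks like randomised support for the premise of the trial (parametrial extension below 1%, Protocol 2.1.1) when it carries almost no information on it. The p-value misleads in both directions. A small one would suggest less parametrial disease after simple hysterectomy, and a large one would suggest similar disease in the two arms. The data could support neither reading.

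**Working it through.** **Inputs.** 350 women per arm (Protocol 14.3). Parametrial rates of 0.4%, 0.6% and 0.63% from the retrospective series in Protocol 2.2.2, and below 1% from Protocol 2.1.1. Two-sided Fisher test and exact intervals (SAP 7.5.7), taking 5% and 95% as the levels.

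**The plan's own figure.** The documents give no power or sample size for this endpoint, so only the arm size can be checked. For the primary test, with 4% in each arm, a 4-point margin and one-sided 0.05: SE = √(2 × 0.04 × 0.96 / 350) = 0.0148, and power = Φ(0.04/0.0148 − 1.645) = 85.4%. This reproduces the stated 85% or so.

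**Step 1: what the simple arm would report.** With no parametrium examined, the result is 0/350. The exact 95% upper limit is 1 − 0.025^(1/350) = 1.05%.

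**Step 2: what counts as significant.** For k cases against 0 with 350 per arm, the two-sided Fisher p is 2 × ∏(350 − i)/(700 − i) for i = 0 to k − 1.
- k = 4: p = 0.124
- k = 5: p = 0.062
- k = 6: p = 0.031

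Six positive radical specimens (6/350 = 1.7%) are enough. SAP 2.1 mentions 750 randomised women; with 375 per arm the p-values for k = 5 and 6 are again 0.062 and 0.031.

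**Step 3: how often that happens with no true difference.** Assume the same true rate π in both arms, with detection in the radical arm only. The chance of p < 0.05 is P(X ≥ 6) for X ~ Binomial(350, π). Two comparisons are shown: 10% of simple-arm women assessable (an assumption, standing for crossovers), and both arms fully assessable.

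| True rate π | Expected radical-arm cases (350π) | Simple arm not assessable | 10% of simple arm assessable | Both arms assessable |
|---|---|---|---|---|
| 0.4% | 1.4 | 0.3% | 0.3% | 0.2% |
| 0.6% | 2.1 | 2.0% | 1.7% | 0.6% |
| 0.63% | 2.2 | 2.5% | 2.0% | 0.6% |
| 1% | 3.5 | 14.1% | 10.6% | 1.5% |

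**Step 4: the per-protocol repeat.** SAP 6 assigns per-protocol women to the operation they received. The simple group is then defined by the procedure that leaves the parametrium behind, so crossovers no longer add assessable women to it. SAP 6 also excludes women with intraoperative findings of pelvic disease, another way in which parametrial disease might have come to light. The repeat has the same fault in a purer form.

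**Step 5: the restricted rate.** If all women are treated as assigned, about 350 radical specimens are assessable. Two cases would give 2/350 = 0.57%, exact 95% interval 0.07% to 2.05%. This is what the trial can say about parametrial spread.

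**The case against.** The strongest reply is that little turns on this row. It is a pathology rate with no power statement and no decision rule. The radical column of Table 31 already gives nearly the right estimate if adherence is high, and Table 18 reports the item by surgery received. Readers also know that simple hysterectomy leaves the parametrium. At the cited series rates, a significant p-value would appear less often than the nominal 5%. All of this stands, and it limits the weight of the point. It does not rescue the simple column, its interval or the p-value. Nor does Table 18 settle the matter while its shell has no row for 'not applicable'.

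A reader might infer more than the documents support:

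- *That the protocol means only to observe this rate.* Protocol 1.2 says so, but Protocol 14.1, Protocol 2.2.3 and SAP 3.2 speak of comparing it. The documents are inconsistent.
- *That the simple arm is zero by construction.* Table 6 allows for crossover, and Table 14 has a row for hysterectomy with parametrium under both operations. SAP 7.4.8 lists the parametrium as a possible site of disease. A few intention-to-treat women in the simple arm could have a recorded value.
- *That a pooled rate would be halved.* Table 31 has no total column and no pooled rate is planned.
- *That false significance is likely.* At a true rate of 2% the chance would be 70%, but 2% is an assumption above the protocol's figure of less than 1%.
- *That the artefact must favour simple hysterectomy.* Six or more positive radical specimens could equally be read as a sign of disease left behind.

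**Conclusion.** The comparison is wrong as written. For women treated as assigned, the parametrial rate in the simple arm will be about 0% whatever the disease, and neither a significant nor a non-significant p-value can be interpreted. The main harm is the estimate: 0/350 with an upper limit of about 1.05%, which is false precision about tissue that was almost never examined. A falsely significant test is the lesser problem: about 0.3% to 2.5% at the cited 0.4% to 0.63%, rising to 14% at the 1% ceiling.

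These figures assume 350 per arm, equal true rates, and no or few assessable women in the simple arm. The 0.4% and 0.6% series figures come from node-negative women, so the trial's own rate could differ. The primary non-inferiority analysis is untouched. This is a fault in one secondary endpoint that should be corrected before the tables are produced; it does not threaten the trial's main conclusion.

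**What to change.** - In SAP 7.5.7, Table 31 and Protocol 14.2, report parametrial involvement descriptively, with an exact confidence interval, among women whose specimen contained parametrium. The 'hysterectomy with parametrium' item of Table 14 identifies them.
- Drop the between-arm Fisher test for this row, in both the intention-to-treat and the per-protocol block.
- Show the number of women for whom the item is not applicable, and restore that row in Table 18 so that it matches SAP 7.4.5.
- Reconcile Protocol 14.1 and SAP 3.2, which list this rate as a comparison, with Protocol 1.2, which lists it as a rate to observe.

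The cost is wording in the SAP, the table shells and the protocol. The SAP already lists the fields needed. What is given up is a p-value that has no valid interpretation.
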